## 1. Trial Summary

The trial is a substantial pragmatic parallel two arm prospective clustered randomised controlled trial to evaluate efficacy of a novel school-based Hindi comic body image intervention in a rural India setting. Schools will be randomised to control or intervention (randomisation with minimisation with target 1:1 with error component). The trial design and its rationale are fully documented in the trial protocol document and in the published study protocol manuscript (Lewis-Smith, H., Hasan, F., Ahuja, L., White, P., & Diedrichs, P. (2022). A comic-based body image intervention for adolescents in semi-rural Indian schools: Study protocol for a randomized controlled trial. *Body Image*).

This document is concerned with the data analysis of the accruing data for the study. The statistical analysis of the study is performed in accordance with the principles stated in the CONSORT guideline statement, with due regard to the SPIRIT guidelines (see Annex 1), and in keeping with Consensus Guideline E9 (Statistical Principles for Clinical Trials) of the International Conference on Harmonisation (ICH).

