### 3 Randomisation

Participants will be randomized to either the intervention or control arm at the school level. Randomization will be conducted at the school level to avoid potential spill over effects within a school. Eligible schools will be randomised in a target 1:1 ratio using minimisation with a residual error. The minimisation factors are (i) number of students at grade 6, 7 or 8 and (ii) proportion of boys at grade 6, 7, and 8. The first 8 schools will be allocated using blocked randomisation thereafter probabilistic minimisation will occur with the probability of minimising set to 0.8. Randomisation will be done in the UK.

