### 4 Endpoints

#### 4.1 Primary Endpoint:

To assess whether there are significant differences in body esteem between randomized groups at T2 after controlling for baseline measure of body esteem.

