### 5 Sample Size

The study design comprises two independent groups with data collected at three time points (T1, T2, T3). The resulting data is amenable to standard analysis for two group comparisons including a 2 by 2 by 2 by mixed factorial design with randomised group as a two level between subjects fixed factor, trial phase (T2, T3) as a longitudinal two-level repeated measures factor, gender as a two-level fixed factor and with commensurate baseline measure (T1) as a mean adjusted covariate. This may be assessed as a classic factorial ANCOVA for a 2 by 2 by 2 mixed design or using a random intercepts mixed linear model capturing the full factorial structure. The model will additionally include school as a random factor, and a sensitivity analysis relating to the inclusion-exclusion of this effect will be conducted

The evaluation of *Confident Me* in an urban Indian setting indicated a range of effect sizes for outcome measures with standardized effects in the small to medium range and exceeding an effect size of  $d = 0.2$ , which would minimally be of interest to public health policy makers. For a lower bound of  $d = 0.2$ , a sample size of  $n = 540$  boys and  $n = 540$  girls per arm would have 95% power to detect an effect separately for each gender (two-sided,  $\alpha = 0.05$ ). To account for 10% loss, the sample size will be inflated by  $(540/10 =) 54$  of each gender per arm, and to account for 10% loss within this additional recruitment, a further inflation of  $(54/10 =) 6$  to give a target sample size of 600 boys and 600 girls per arm, totalling 1,200 per arm (intervention versus control). Therefore, a total of 2,400 students will be recruited. Students will be equally divided across years 6, 7, and 8, and gender.

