## Statistical Analysis Plan

---

sensitivity analysis will be undertaken to better understand the data. As appropriate, missing data sensitivity analyses will be performed on both the ITT **analysis** set and the PP **analysis** set.

In general, all statistical tests will be performed as two-sided tests with a nominal significance level of  $\alpha = 0.05$  and effect sizes reported.

There is no planned interim analysis for trial progression but there will regular reports to the trial steering committee and trial management group for oversight.

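### The stated 95% power per gender makes no allowance for randomising schools and is not supported by the SAP's own inputs; the size of the loss cannot be determined from the SAP

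*SAP*

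**What the plan says.** Section 1 describes a "pragmatic parallel two arm prospective clustered randomised controlled trial". Section 3 is equally clear: "Participants will be randomized to either the intervention or control arm at the school level", and the reason given is contamination: "Randomization will be conducted at the school level to avoid potential spill over effects within a school". The primary model in section 6.1 (Primary outcome) has school as a random factor and the baseline score as a covariate.

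Section 5 opens on a different footing: "The study design comprises two independent groups with data collected at three time points (T1, T2, T3"). It takes d = 0.2 as the lower bound of interest and arrives at 540 boys and 540 girls per arm, with the claim that 540 "girls per arm would have 95% power to detect an effect separately for each gender" at two-sided 0.05. It then adds 54 and 6 for 10% loss, giving 600 per gender per arm and 2,400 in all. School is mentioned in section 5 only as a term in the analysis model. No ICC, design effect, number of schools or cluster size enters the calculation, and no baseline correlation is stated.

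The primary endpoint in section 4.1 is the comparison of arms at T2: "To assess whether there are significant differences in body esteem between randomized groups at T2 after controlling for baseline measure of body esteem". Section 5 states power only for each gender separately.

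**The concern.** When schools are allocated, pupils in the same school tend to resemble each other, and each pupil adds less information than an independent one. The variance of the arm difference rises by the design effect, 1 + (m − 1) × ICC, where m is the number of analysed pupils per school. A calculation without this term answers a question about a different design.

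The stated power matters for interpretation. Gender-split comparisons are planned at T2 and T3. A non-significant result in boys or in girls would be set against a claimed 95% power at d = 0.2, the effect that section 5 calls the minimum of interest to policy makers. If the true power is materially lower, that reading would be wrong.

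**Working it through.** **Inputs from the SAP.** d = 0.2 (SD = 1), 540 evaluable per gender per arm, alpha 0.05 two-sided (section 5; section 6 confirms that "all statistical tests will be performed as two-sided tests with a nominal significance level of" 0.05), schools randomised 1:1 (section 3).

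**Step 1: the SAP's own figure, no clustering.**
- n per group for 95% power, two-sided: 2 × (1.960 + 1.645)² / 0.2² = 650.
- Power at n = 540: 0.2 × √(540/2) = 3.286, and Φ(3.286 − 1.960) = 90.8%.
- Power at n = 540, one-sided: Φ(3.286 − 1.645) = 95.0%.
- Loss: 540 / 0.9 = 600, as stated.

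So 540 matches 95% only as a one-sided calculation for independent pupils. The sidedness is a separate slip, but it shows that 540 contains no hidden margin for clustering: it is already below the 650 needed with a design effect of 1.

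**Step 2: add clustering.** The SAP gives none of the following, so these are assumptions: K = 12, 20, 40 or 60 schools in total (section 3 implies more than 8), equal school sizes, ICC 0.01 to 0.05, and baseline-outcome correlation r = 0 or 0.6, removing r² = 36% of the variance at both pupil and school level.
- m = 540 / (K/2)
- DE = 1 + (m − 1) × ICC
- SE = √(2 × DE × (1 − r²) / 540)
- Power from the noncentral t with K − 2 degrees of freedom and noncentrality 0.2 / SE.

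Worked case, K = 20 and ICC = 0.02: m = 54; DE = 1 + 53 × 0.02 = 2.06; SE = √(2 × 2.06/540) = 0.0873; noncentrality 2.29 against a critical value of 2.10 on 18 df; power 58%. With r = 0.6, SE = 0.0873 × 0.8 = 0.0699, noncentrality 2.86, power 77%.

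Power per gender (%), at ICC 0.01 / 0.02 / 0.03 / 0.05:

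| Schools | m per gender | r = 0 | r = 0.6 |
|---|---|---|---|
| 12 | 90 | 58 / 43 / 34 / 25 | 77 / 60 / 49 / 36 |
| 20 | 54 | 71 / 58 / 49 / 37 | 88 / 77 / 68 / 53 |
| 40 | 27 | 81 / 74 / 67 / 56 | 95 / 90 / 85 / 75 |
| 60 | 18 | 85 / 80 / 75 / 66 | 96 / 94 / 91 / 84 |

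**Step 3: the pooled T2 comparison.** There are 1,080 pupils per arm but the same number of schools, so m doubles. The same ICC is assumed for the pooled sample. With 20 schools (m = 108), power is 86 / 70 / 57 / 42% unadjusted and 97 / 87 / 76 / 59% with r = 0.6. With 40 schools and r = 0.6 it is 99.6 / 98 / 94 / 84%. With independent pupils it would be 99.6%.

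**The case against.** The strongest reply is baseline adjustment. The planned model includes the baseline score, and section 3 sets no upper limit on schools. With r = 0.6 and ICC 0.01, power per gender is about 95% with 40 schools and 96% with 60. At ICC 0.005 with 20 schools and r = 0.6 it is 93%. This stands as far as it goes: favourable values could bring the trial to about 95%. It does not rescue the statement in section 5, which neither states a correlation nor claims credit for one.

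The reference distribution is also a choice. The SAP plans a mixed model with a log-likelihood comparison, and a normal approximation gives higher figures (20 schools, unadjusted: 76% and 63% at ICC 0.01 and 0.02, against 71% and 58% here). Part of the loss shown therefore comes from the t reference, which is defensible when schools are few. The normal approximation also stays below 91% at any positive ICC without baseline credit.

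It is fair to add that clustering is handled in the planned inference, because school is in the model, and that Cohen's d is to be reported with a 95% confidence interval, which reduces the risk of misreading a null result. School numbers may be in the protocol, which is not at hand. The 95% claim, however, is made in the SAP from inputs that it lists. Finally, the missing power for the pooled T2 endpoint is only a reporting gap: pooled power exceeds power per gender in every matching scenario above.

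**Conclusion.** The point holds as a statement about what section 5 supports. Its 95% power per gender rests on independent pupils, makes no allowance for clustering, and does not follow from the stated inputs. Without baseline credit no positive ICC can reach 95%, because the two-sided ceiling at ICC 0 is about 91%.

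A reader might go on to infer that the trial lacks 95% power, or that its real power is some particular figure such as half to three quarters. The SAP does not support either. It gives no ICC, number of schools or baseline correlation, and over the assumed ranges power per gender runs from 25% (12 schools, ICC 0.05, unadjusted) to 96% (60 schools, ICC 0.01, r = 0.6). These figures assume equal school sizes, d = 0.2, 540 evaluable per gender per arm, a t reference with schools minus 2 df and, where r = 0.6 is used, equal variance reduction at both levels.

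**What to change.** Keep 2,400 pupils. In section 5, remove the unqualified 95% and restate power, or the minimum detectable d, at two-sided 0.05. State the expected number of schools, the pupils per school and gender, an ICC range such as 0.01 to 0.05, the design effect 1 + (m − 1) × ICC, and the baseline correlation for which credit is taken. Give the result for the pooled T2 primary endpoint and for each gender.

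The cost is one calculation and a revised paragraph, with no extra pupils and no change to the analysis. The drawback is that the stated power will probably be less favourable than the present figure.

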### 6 Analysis Plan

The data analysis plan for the primary outcome measure will be the same plan for all secondary outcome measures.

A review, verification and validation (RVV) for data integrity will be performed prior to any inferential analysis. This review will include data screening for any potentially influential observations or groups of observations which might otherwise compromise robust statistical conclusions. This review is for data correction and will conform to intent to treat principles.

The data will also be screened for missing data. It is anticipated that data will be missing completely at random with non-school attendance independent of the study will be the main source of missingness. For this reason, (i) an ITT analysis will use all available data via a linear mixed model and (ii) a per protocol analysis. The per protocol analysis set will comprise those who provide outcome data and pass attention control checks. If statistical conclusions are sensitive to the analysis data set and approaches then a

## Statistical Analysis Plan

---

sensitivity analysis will be undertaken to better understand the data. As appropriate, missing data sensitivity analyses will be performed on both the ITT **analysis** set and the PP **analysis** set.

In general, all statistical tests will be performed as two-sided tests with a nominal significance level of  $\alpha = 0.05$  and effect sizes reported.

There is no planned interim analysis for trial progression but there will regular reports to the trial steering committee and trial management group for oversight.

### 6.1 Primary outcome

The primary outcome of body image will be measured using the Body Esteem Scale for Adults and Adolescents. The BESAA is comprised of three subscales (*Appearance, Weight and Attribution*) and asks participants about their thoughts and feelings in relation to their body and appearance. Responses to items will be indicated using a 5-point Likert scale, ranging from 1 (*Never*) to 5 (*Always*), with higher scores indicating greater dissatisfaction. Only the combined mean scores for the Appearance and Weight subscales will be used in analyses, as the Attribution subscale relates to the perception of others' attitudes towards one's appearance. The English language BESAA has demonstrated good internal and re-test reliability and construct validity among Indian adolescents and other globally diverse adolescent samples. A Hindi version of the scale will be used in this study.

Table 4.1 summarises the descriptive statistics that will be extracted for BESSA. These data will be further summarised graphically using box-and-whisker plots, error bar graphics, scatterplots and similar as appropriate. Effect size will be calculated using Cohen's *d* and 95% confidence intervals for Cohen's *d* will also be given. Percentages reporting positive change, no change, and a poorer outcome, along with 95% confidence intervals will be reported.

The primary analysis will be a linear mixed model with random intercepts with school declared as a random factor. The model will additionally include the three main effects, three two-way interactions, and the three-way interaction for randomised arm (between subjects fixed effect factor with 2 levels comic intervention and control), study phase (repeated measures fixed effect factor with two levels T2 and T3), gender (between subjects fixed effects factor with 2 levels, male and female) and include a baseline measure as a covariate, and the three two-way interactions between covariate and each of randomised arm, gender, and phase). An overall assessment of the contribution of randomised arm to the model will be undertaken using the change in the log-likelihood statistic between its inclusion and exclusion from the model. Post hoc analyses will proceed primarily comparing the two randomised arms at T2 controlling for baseline covariate

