#### 4.2 Secondary Endpoints:

The data analysis plan for the primary outcome measure will be the same plan for all secondary outcome measures.

- (a) To assess changes in all outcome measures and their subscales over the study duration (between T1, T2, and T3) within each randomised arm.
- (b) To assess whether outcomes measures at T2 differ between randomised arms after controlling for commensurate baseline scores
- (c) To assess whether outcomes measures at T3 differ between randomised arms after controlling for commensurate baseline scores
- (d) To assess whether outcome measures change between T2 and T3 and whether any changes are dependent on randomised arm after controlling for commensurate baseline scores
- (e) To assess whether any differences in measures at T2 between randomised arms are gender specific after controlling for commensurate baseline scores
- (f) To assess whether any differences in measures at T3 between randomised arms are gender specific after controlling for commensurate baseline scores
- (g) To assess whether interventional changes in Body Esteem between T1 and T3, and Body Esteem at T3, are mediated by changes in internalisation of appearance ideals between T1 and T2, and whether mediation is gender dependent.

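### With school entered only as an intercept, the arm-by-phase test behind secondary endpoint (d) uses pupil-level error and holds 5% only if schools do not differ in their T2-to-T3 change

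*SAP*

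**What the plan says.** **Unit of randomisation.** SAP section 3: "Participants will be randomized to either the intervention or control arm at the school level". The proportion of boys in the school is one of the two minimisation factors.

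**Random part.** Section 6.1: "The primary analysis will be a linear mixed model with random intercepts with school declared as a random factor". Section 5 describes a random-intercepts mixed model and continues: "The model will additionally include school as a random factor, and a sensitivity analysis relating to the inclusion-exclusion of this effect will be conducted". Neither section has a school-by-phase or school-by-gender term, a cluster-robust standard error, or degrees of freedom based on the number of schools.

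**Fixed part.** Section 6.1: "The model will additionally include the three main effects, three two-way interactions, and the three-way interaction for randomised arm", phase ("repeated measures fixed effect factor with two levels T2 and T3") and gender, plus the baseline score and its interactions. Arm as a whole is assessed by the change in log-likelihood when it is left out. Comparisons at T2 and then at T3 follow: ignoring gender, split by gender, and with gender as a factor.

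**Question served.** Secondary endpoint 4.2(d) asks whether measures change between T2 and T3 and "whether any changes are dependent on randomised arm after controlling for commensurate baseline scores". In this model that is the arm-by-phase term. The same plan applies to every secondary outcome.

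**The concern.** When schools are randomised, every comparison of arms has to be judged against variation between schools. A random school intercept does this for the level of the outcome. It does not do so for a within-school contrast such as T3 minus T2, because a constant school effect subtracts out. The model as written therefore assumes that all schools in an arm share the same true change between T2 and T3. Section 2 puts those visits 11 weeks apart, so schools could differ in term timing, examinations or staff over that interval. Any such difference goes into the pupil residual, and the test behaves as if about 2,000 pupils had been randomised separately.

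At stake is the conclusion that an effect fades or grows after T2, for BESAA and for five secondary measures. The same cancellation affects arm by gender where boys and girls share a school.

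**Working it through.** **No figure to reproduce.** The SAP states only the nominal two-sided 0.05 for these tests.

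**Inputs from the SAP.** Schools are randomised; the phases are T2 and T3; 540 boys and 540 girls per arm are expected after losses, so 1,080 per arm and 2,160 in all.

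**Inputs assumed (not in the SAP).** 20 or 40 schools (2,160/20 = 108 or 2,160/40 = 54 pupils each); total variance 1 after baseline adjustment; school ICC 0.01 or 0.02; within-pupil T2–T3 correlation 0.6; correlation *r* of a school's effect between T2 and T3 of 0.9, 0.8 or 0.6.

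**Step 1: what the model tests.** With pupil and school intercepts, both cancel from T3 minus T2. Arm by phase becomes a comparison of pupil changes between arms.

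**Step 2: variance components.**
- School-by-phase: s²_sp = ICC × (1 − r)
- Pupil residual: s²_e = (1 − ICC) × (1 − 0.6)

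**Step 3: true variance over assumed variance**, with m pupils per school:

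ratio = 1 + (m − 1) × s²_sp / (s²_sp + s²_e)

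**Step 4: true size** = 2 × [1 − Φ(1.96 / √ratio)].

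**Worked case** (ICC 0.02, r = 0.8, 20 schools): s²_sp = 0.02 × 0.2 = 0.004; s²_e = 0.98 × 0.4 = 0.392; ratio = 1 + 107 × 0.004/0.396 = 2.08; size = 2 × [1 − Φ(1.96/1.44)] = 17.4%.

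| ICC | Schools | r = 1 | r = 0.9 | r = 0.8 | r = 0.6 |
|---|---|---|---|---|---|
| 0.01 | 40 | 5.0% | 6.6% | 8.2% | 11.3% |
| 0.01 | 20 | 5.0% | 8.2% | 11.4% | 17.3% |
| 0.02 | 40 | 5.0% | 8.2% | 11.4% | 17.2% |
| 0.02 | 20 | 5.0% | 11.5% | 17.4% | 26.9% |

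The within-pupil correlation matters too. At 0.4 the worked case has s²_e = 0.98 × 0.6 = 0.588 and ratio 1 + 107 × 0.004/0.592 = 1.72, a size of about 13.5%.

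**Step 5: simulation.** With ICC 0.02 and r = 0.8, 4,000 simulated null trials gave 18.0% (20 schools) and 12.1% (40 schools). A school-level test of the same contrast gave 5.1% and 4.9%. With no school-by-phase variance, the pupil-level test gave 5.1%.

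**Step 6: overall likelihood test.** If arm is removed with its interactions, five terms go, arm by phase among them. With school-by-phase variance 0.01 and pupil and residual variances of 0.5 each, simulated null rejection was about 11% (40 schools), 18% (24) and 23% (16). The implied ICC of the change is 0.01/0.51 = 0.0196. That is near the top of the range above; the worked case has 0.004/0.396 = 0.0101.

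**Step 7: arm by gender at one time point.** Assume mixed schools with 54 boys and 54 girls (20 schools) and pupil variance 0.98.
- School-by-gender variance 0.004: ratio 1 + 53 × 0.004/0.984 = 1.22, size 7.5%.
- Variance 0.01: ratio 1 + 53 × 0.01/0.99 = 1.54, size 11.4%.

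**Step 8: T2 contrast.** With the school intercept in the model, simulated size was about 5% to 9% across the settings examined. The upper part of that range used a normal reference with no small-sample correction.

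**The case against.** **The primary endpoint is not at risk here.** It is the arm difference at T2, which the school intercept largely covers. This stands, provided school stays in that comparison. A reader might infer from the likelihood-test figures that the primary result is invalid; Step 8 does not support that.

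**The inflation is assumed, not shown.** This also stands. The SAP gives none of the inputs, and with no school-by-phase variance the test is correct. It would be too strong to say that the test must reject far more than 5% of the time: at ICC 0.01, 40 schools and r = 0.9 the figure is 6.6%.

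**The random part might be read as school only.** Then within-pupil correlation is ignored and the standard error is about √(1/0.4) = 1.58 times too large at correlation 0.6, which makes the test conservative when schools do not differ in change. One might conclude that the SAP is wrong on either reading. But section 5 describes a random-intercepts model to which school is added ("The model will additionally include school as a random factor"), and phase is a repeated-measures factor, so pupil intercepts are the natural reading. On that reading the error is wrong only if schools differ in their change.

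**Endpoints (e) and (f) do not rest only on the joint model.** The single-time-point comparisons in section 6.1 also address them. That is fair, but if those comparisons carry only a school intercept, arm by gender has the same weakness in mixed schools. The minimisation factor "proportion of boys at grade 6, 7, and 8" suggests that some schools are mixed without saying so. In single-sex schools the intercept already covers gender.

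**Other safeguards exist.** They do not reach this point. With pupil intercepts in the model, keeping or dropping school leaves the T2-to-T3 contrast essentially unchanged, so agreement between the two fits would reassure wrongly. False discovery rate control takes the p-values as valid. The general check of model assumptions names no test for school-by-phase variation.

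**Conclusion.** The point holds for arm by phase. As specified, endpoint 4.2(d) is tested against pupil-level error in a trial that randomised schools, and the nominal 5% is right only if schools do not differ in their T2-to-T3 change. Under the stated assumptions the true level is about 6.6% to 27%. The overall likelihood test shares the fault to the extent that it drops arm by phase. For arm by gender the fault is smaller, about 7.5% to 11%, and conditional on mixed-sex schools. This should be corrected before analysis. It does not overturn the primary comparison at T2, nor the T3 comparison in 4.2(c), which is likewise a single-time contrast that a school intercept accommodates.

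**What to change.** In section 6.1, state the random effects in full: pupil within school, school, and school-by-phase. Test arm by phase with degrees of freedom based on the number of schools, or equivalently analyse school mean changes from T2 to T3. Where schools are mixed-sex, add school-by-gender for the arm-by-gender tests, including those at a single time point. Say which terms leave the model in the overall likelihood test of arm, and run that test with the school-by-phase term in both fits. If a variance component is estimated at zero it may be dropped from the fit, but the school-based degrees of freedom should be kept.

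The cost is a sentence or two and no new data. If schools do not differ in their change, interaction intervals widen only slightly, through the degrees of freedom. If they do differ, the intervals widen by about the square root of the ratio in Step 3 (√2.08 = 1.44 in the worked case), which is the width the design requires. Zero variance estimates will occur now and then.

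### The SAP tests randomised arm by a log-likelihood change and states no small-sample degrees-of-freedom method for that test or for the primary T2 contrast, although arm is allocated by school

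*SAP*

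**What the plan says.** Section 3 makes the school the unit of allocation: "Participants will be randomized to either the intervention or control arm at the school level". It does not give the number of schools. It shows only that there are more than eight: "The first 8 schools will be allocated using blocked randomisation thereafter probabilistic minimisation will occur".

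Section 6.1 (Primary outcome) models the clustering: "The primary analysis will be a linear mixed model with random intercepts with school declared as a random factor". The fixed part holds arm, phase (T2, T3) and gender with all their interactions, the baseline score, and "the three two-way interactions between covariate and each of randomised arm, gender, and phase". It continues: "An overall assessment of the contribution of randomised arm to the model will be undertaken". The statistic named for this purpose is the "change in the log-likelihood statistic between its inclusion and exclusion from the model".

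The primary endpoint in section 4.1 is narrower: "significant differences in body esteem between randomized groups at T2 after controlling for baseline measure of body esteem". Section 6.1 reaches it by a further step: "Post hoc analyses will proceed primarily comparing the two randomised arms at T2 controlling for baseline covariate". It calls these follow-up comparisons ANCOVA and reports partial eta squared.

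Nowhere does the SAP state maximum likelihood (ML) or REML, a reference distribution for the log-likelihood change, which arm terms are removed, or a df method for either comparison. Section 6 sets a two-sided nominal level of 0.05 and applies the same plan to every secondary outcome.

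**The concern.** The arm main effect varies only between schools. Its error df come from the number of schools, not from the 2,400 pupils. A log-likelihood comparison of models with different fixed effects requires ML, because REML likelihoods are not comparable across different fixed parts. ML makes no allowance for the fixed effects estimated at school level and so underestimates the between-school variance. The customary chi-square reference then treats that variance as known. Both push towards rejection. A school random intercept models the clustering but does not remove this small-sample error.

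The T2 contrast is exposed in the same way if its standard error is used with a normal reference, or with an F whose denominator df count pupils. At stake is whether the nominal 5% level holds for the primary comparison and for the secondary outcomes, whose p-values then enter the false discovery rate procedure in section 6.5.

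**Working it through.** **Inputs.** From the SAP: two-sided α = 0.05 (section 6); arm allocated by school (section 3); the model terms (section 6.1). Assumed, because not stated: number of schools K from 10 to 100; equal school sizes; equal arms; chi-square reference.

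**Arm terms in the model.** Arm, arm × phase, arm × gender, arm × phase × gender and arm × baseline: five in all. Only the main effect is purely between schools.

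**Benchmark.** In the balanced case a t reference on K − 2 df for the arm effect returns exactly the planned 5.0%. The question is how far the other references depart from it.

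**(a) Only the arm main effect dropped (1 df).** With equal school sizes and a positive school variance, the ML likelihood-ratio statistic is

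LRT = K · ln(1 + t²/(K − 2)), with t on K − 2 df.

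It is compared with 3.841. For K = 20, LRT > 3.841 means t² > 18 × (exp(3.841/20) − 1) = 18 × 0.2118 = 3.81, so |t| > 1.952. On 18 df that has probability 6.7%.

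**(b) All five arm terms dropped (5 df).** The four remaining terms are informed largely within schools, so their share is taken as an independent chi-square on 4 df:

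P[ K · ln(1 + t²/(K − 2)) + χ²₄ > 11.07 ].

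**(c) T2 contrast against a normal reference.** P(|t| > 1.96) on K − 2 df.

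| Schools (K) | (b) five terms | (a) main effect only | (c) T2, normal reference |
|---|---|---|---|
| 10 | 6.6% | 8.9% | 8.6% |
| 20 | 5.6% | 6.7% | 6.6% |
| 40 | 5.3% | 5.8% | 5.7% |
| 100 | 5.1% | 5.3% | 5.3% |

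**Check by simulation.** The SAP's model was simulated under no effect: 2,160 pupils (the 2,400 target less 10% loss), two phases, school and pupil intercepts, intraclass correlation 0.01 to 0.10 (assumed), 2,000 runs per setting, Monte Carlo standard error about 0.5 percentage points. Ranges are across the intraclass correlations.

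| Schools | Five terms | Main effect only |
|---|---|---|
| 10 | 5.9–7.8% | 7.9–9.3% |
| 20 | 5.7–6.5% | 6.0–7.8% |
| 30 | 4.8–6.1% | 5.4–6.0% |
| 60 | 5.1–5.8% | 5.4–6.3% |

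These agree with the formulas within simulation error. On the five-term reading the excess is hard to tell from that error at 30 schools and above. The simulation assumes equal school sizes, mixed-gender schools, complete data, and no school-by-phase or school-by-gender variation.

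**The case against.** The strongest reply is that the SAP does not state the faulty test. It names no chi-square reference and no estimation method, so a careful analyst could still apply a corrected one. That stands: chi-square is the default for this statistic, but attributing it to the SAP is an inference.

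A reader might infer that the trial has few schools and that a type I error above 5% is demonstrated. The document does not support this. It implies only more than eight schools, and the count may properly sit in the protocol. With many schools the excess is negligible.

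A reader might also take the 1-df figures as the main result. Removing arm while keeping its interactions is an odd test of arm's contribution, so the five-term reading is the more natural one, and its excess is smaller.

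Nor is the log-likelihood change the test of the primary endpoint. Section 6.1 presents it as an overall assessment and does not make it a gate for the T2 comparison. The ANCOVA and partial eta squared wording suggests F tests there, not a normal reference. This stands in part: an F test protects the level only if its denominator df reflect schools. On pupil-level residual df it is practically the normal reference, and the SAP does not say which applies.

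Finally, it would be tempting to say that the planned confidence intervals are too narrow. The intervals the SAP names are for Cohen's d and for percentages changed. None is tied to the likelihood-ratio test, so that claim has no basis.

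**Conclusion.** The concern holds as a gap in method, not as a proven error rate. The SAP chooses a log-likelihood comparison for a school-allocated effect and fixes no small-sample df method, either for it or for the T2 contrast that decides the primary endpoint. Under the default chi-square reading the excess over 5% on the five-term test runs from about 1.6 percentage points at 10 schools to 0.1 at 100. For the main effect alone it runs from 3.9 to 0.3, and for a T2 contrast on a normal reference from 3.6 to 0.3. These figures rest on balanced schools and an assumed school count.

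The document does not support a stronger conclusion, such as that the trial will miss its 5% level materially or that clustering is ignored: school is in the model as a random intercept. This is a cheap improvement.

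**What to change.** In section 6.1, state that the mixed model is fitted by REML with school kept as a random effect. Base the primary inference on the T2 arm contrast from that model with Kenward-Roger or Satterthwaite df, and report the matching 95% confidence interval.

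These df are estimated from the fitted variances and can rise well above the between-school value when the estimated school variance is close to zero. For that case, pre-specify a between-school t reference on the number of schools minus 2 df, with the triggering condition defined in advance.

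If the overall assessment of arm is kept, list the arm terms it removes and make it an F test of those terms with the same df method. Apply the same rule to the secondary outcomes. Stating the number of schools, or pointing to where the protocol gives it, would let a reader judge how much this matters.

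The cost is a sentence or two and a standard software option. The downside is slightly wider intervals: with 20 schools the multiplier on 18 df is 2.101 instead of 1.960, a ratio of 1.07; with 100 schools it is 1.984, a ratio of 1.01. With many schools the change does no harm.
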